Research Protocol

Using mental imagination to prevent excessive gestational weight gain in overweight and obese pregnant women

I. Objectives

1. To determine feasibility of the goal-oriented intervention: recruitment, randomization, retention, and intervention implementation.
2. To investigate the potential efficacy of the intervention on gestational weight gain (primary outcome) and maternal and birth outcomes (secondary outcomes: gestational diabetes, gestational hypertension, mode of delivery, length of labor, apgar score, new born body weight, and premature baby).

Primary hypothesis. A higher proportion of intervention participants will have healthy gestational weight gain than the usual prenatal care participants

Secondary hypothesis. A lower proportion of intervention participants will have gestational diabetes, gestational hypertension, cesarean delivery, premature birth, longer duration of labor, unhealthy birth weight (>4000 or < 2500 grams), premature birth, and APPGAR score ≤ 3 than the usual prenatal care participants.

3. To investigate the potential impact of the intervention on lifestyle behaviors: diet (caloric, fat, sugary drink, fruit and vegetable intakes) and physical activity (walking steps and energy expenditure).

Hypothesis 1. A higher proportion of intervention participants will eat healthier than the usual prenatal care participants.

Hypothesis 2. A higher proportion of intervention participants will have more walking steps and higher energy expenditure than the usual prenatal care participants.

4. To investigate the potential intervention effects on motivation (autonomous motivation, self-efficacy, consideration of future, happiness, and hope), emotion (emotion control, stress, and depressive symptoms), cognition (executive function and impulsiveness) and psychological eating (cognitive restraint eating, emotional eating, overeating and eating out of boredom)

Hypothesis 1. A higher proportion of intervention participants will have higher motivation and self-efficacy, better emotion, higher cognition, and lower psychological eating than the usual prenatal care participants.

[figure not shown]
II. Background and Rationale

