A.1. Overweight or obese pregnant women. Nearly 56% of American women aged 20-39 are overweight or obese.¹ These women are at least two times more likely than normal weight women (65-85% for overweight or obese vs. 34% for normal weight) to experience excessive gestational weight gain (EGWG),²⁻⁸ exceeding Institute of Medicine (IOM) pregnancy weight gain guidelines.⁹ EGGW is a serious public health problem because it negatively influences maternal and birth outcomes: gestational diabetes,¹⁰ gestational hypertension,¹¹ cesarean delivery,¹² and fetal macrosomia (birth weight > 4000 gm).^{12,13} EGGW is also a strong predictor of significant postpartum weight retention (retaining ≥ 10 lbs), which is associated with lifelong obesity in mothers¹⁴ and childhood obesity.^{15,16} Pregnancy is a teachable movement for weight management and obesity prevention.¹⁷ Therefore, it is imperative to help overweight or obese pregnant women prevent EGGW.

A.2. Previous lifestyle behavior intervention studies. Healthy lifestyle behaviors (healthy eating and physical activity, **PA**) can prevent EGWG in overweight or obese pregnant women.¹⁸⁻²⁸ Efficacious strategies identified in prior studies involve personalized caloric restriction,²¹⁻²⁵ frequent in-person meeting attendance²²⁻²⁴ or phone counseling^{25,26} and frequent text messages requiring responses.²⁶ Such interventions have limited practicality, scalability, and sustainability due to high participant burden and excessive cost for clinical practice. Also, adherence was problematic,^{22,26,29-31} perhaps because of educational materials and counseling that were prescriptive and not sufficiently flexible or tailored to individuals.³² Moreover, the prior studies paid little or no attention to motivation, emotion and executive function, all of which are crucial for healthy lifestyle behaviors.

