A.4. Scientific premise. The proposed R21 builds on the strengths and addresses limitations of prior studies. **Strengths.** Lifestyle behavior interventions can prevent EGWG, and EFT improves motivation, emotion, ExF, lifestyle behaviors, and weight management. **Limitations.** Prior lifestyle interventions did not apply FTP, which focuses on motivation, emotion and ExF (critical concepts for promoting healthy lifestyle behaviors and health outcomes). Also, they were too prescriptive and time-consuming for participants (difficult to scale and sustain in practice). Prior EFT studies were mainly conducted in lab and only applied episodic simulation. We propose a 20-week self-directed, web-based intervention (35-40 min/week) and include three forms of EFT: episodic simulation, intention (goal setting), and planning (organization of steps for accomplishing a goal).⁹⁶ Our intervention will efficiently apply GOEFT to address motivation, emotion, ExF, lifestyle behaviors and health outcomes (C.3.6). This proposed study will add scientific knowledge in design and delivery of lifestyle interventions aimed to prevent EGWG in overweight or obese pregnant women.

A. Research Design

This proposed pilot randomized controlled trial (RCT) aims to (1) determine feasibility of the GOEFT intervention and investigate the potential efficacy of the intervention on (2) GWG and maternal and birth outcomes, (3) lifestyle behaviors, and (4) motivation, emotion, and cognition. We will enroll 90 overweight or obese pregnant women (50% White, 50% minority). All measures will be assessed at baseline (T1, ≤15 week-gestation), at 24-27 week-gestation (T2) and at 35-37 week-gestation (T3)

B. Sample

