Sample size/power. Our primary outcome variable is weekly gestational weight gain (GWG). A final sample size of 72 women (36 per group, after accounting for 20% attrition from the 90 enrolled) will have 80% power to detect a time-averaged between-group difference in weekly GWG with a medium effect size (standardized between-group difference of 0.6). This effect size is translated to a between-group difference of 0.33 lb in weekly GWG, assuming a common standard deviation of 0.55 lb (or 0.25 kg) based on previous research.²⁷ The power analysis was conducted using mixed-effect linear modeling with a two-sided significance level of 0.05, assuming a correlation of 0.7 between the two weekly GWG measures. Due to the pilot nature of the study, our sample size is not powered to detect smaller effect sizes (<0.6). Nevertheless, we will report point estimates, effect sizes, and 95% confidence intervals. These estimates along with clinical significance will guide the results interpretation and sample size determination for a future full-scale RCT (R01).

C. Measurement/ Instrumentation

All participants will be assessed at ≤ 16 week-gestation (T1), 24-27 week-gestation (T2) and 35-37 week-gestation (T3). Survey data will be collected online using password-protected security-ensured Research Electronic Data Capture (REDCap), a secure web application for building and managing online surveys and databases. Primary and secondary outcomes will be extracted from electronic health record. An incentive of \$40 will be provided for participation in each point of data collection for all measurements.

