Feasibility. We will use our tracking records to assess recruitment, randomization and retention. To assess intervention implementation, we will extract data from our study web site that will track and capture details about all activities (e.g., amount of and type of activities completed and % of participants used type in box). We will record the attendance of individual coaching session. Intervention participants will report their motivation and barriers preventing them from engaging in the intervention activities and evaluate the usefulness of with each EFT intervention component. We will also use semi-structure interview questions (up to 20 minutes/an individual interview via zoom) to ask participants to evaluate the intervention. We will use website tracking data, individual coaching session, and results of phone interview to revise the intervention contents for a future large scale intervention study.

Primary outcome: GWG (in lbs). Body weight or gestational weight gain will be extracted from participants' electronic health record.

To compute weekly GWG, we will subtract the measured weights between two adjacent time points (T2 vs. T1; T3 vs. T2) then divide by the number of weeks between the two time points. The IOM recommends that overweight women (BMI 25.0-29.9) be limited to total GWG of 15-25 lbs and obese women (BMI ≥ 30.0) to 11-20 lbs.⁹ To compute the total GWG, we will subtract the self-reported pre-pregnancy weight from weight measured at T3. A woman will be identified as having excessive gestational weight gain if her total gestational weight gain exceeds the Institute of Medicine's criteria.

Secondary outcomes: gestational diabetes, gestational hypertension, mode of delivery, length of labor, apgar score, new born body weight, and premature baby will be accessed by [name] (Co-I) or research staff from the participants' electronic health record.

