Usual care. All study participants will receive usual prenatal care from their obstetrician or midwife. The usual prenatal care visit occurs monthly until 28 week-gestation, every other week from 28-36 week-gestation and weekly from 36-week until delivery. At our collaborating clinics, pregnant women are weighed at each prenatal visit and will receive additional healthy eating counseling, e.g., if they have GDM. To improve retention of women randomly assigned to the usual care group, we will email study newsletters every other month with general information about pregnancy-related health (e.g., over-the-counter medication).

Intervention: A self-directed, web-based GOEFT lifestyle behavior intervention (tailored to participants' needs). ***Intervention mode.*** Intervention participants will receive all aspects of usual care plus a self-directed, web-based GOEFT lifestyle behavior intervention. Previous self-directed, web-based interventions have effectively promoted weight management in overweight or obese adults.¹²³⁻¹²⁵ Also, EFT has been delivered on the web and shown promise for promoting weight management.^{63,126} ***Intervention duration, dosage and topics.*** The intervention will last 20 weeks (start \leq 17 weeks gestation), a duration effectively preventing EGWG in overweight or obese women.²⁰⁻²⁸ Intervention participants will complete weekly online activities (35-40 min/week) via their smart phone or internet access from any location. The intervention includes *three topics*: stress management, healthy eating, and PA (Figure 2). ***Intervention (long-term) goals.*** Participants are strongly encouraged to (1) daily manage stress and emotional reactions using positive strategies, (2) daily eat a diet low in fat and consume less sugary drinks, (3) daily eat a diet high in fruits and vegetables, and (4) walk at a brisk pace for 30 min most days a week.¹²⁷

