complete ≥ 12 weekly intervention activity with $\geq 80\%$ weekly activities completed; 75% of women will be able to generate good quality of steps to achieve their chosen goals; 80% will use the pre-written goals instead of type in (intervention implementation). **Aim 2**, we will first use descriptive statistics and trend plots to summarize and visually compare the weekly gestation weight gain over time. Mixed-effects linear modeling will be used to model the weekly GWG as a linear function of treatment (intervention vs. usual prenatal care care), time, and treatment by time interaction. From the model, we can derive estimates of the time-averaged weekly gestational weight gain for each group, the between-group difference in weekly gestational weight gain at each time point and adjust for within-subject clustering from repeated measures and covariates (e.g., race). We will use logistic regression to estimate the between-group (intervention vs. usual care) difference in the probability of having a binary outcome (for example, excessive gestational weight gain, gestational hypertension, new born body weight), adjusting for covariates (e.g., race). **Aims 3 and 4**, mixed-effects linear modeling will be used to model each continuous outcome (dietary intakes, PA, and psychological eating for Aim 3; motivation, emotion and cognition for Aim 4) as a linear function of treatment, time, and the treatment by time interaction. The intervention effects will be estimated by between-group comparisons of change in the outcome (e.g., healthy lifestyle behaviors) from baseline. Again, we will adjust for within-subject clustering from repeated measures and covariates (e.g., race) in the mixed-effects regression models. **Missing data**. We will carefully examine the pattern of missing data and conduct appropriate multiple imputation if missing at random is indicated. The mixed-effects modeling allows for missing at random. If missing not at random exists, pattern mixture modeling will be used. Sensitivity analysis will evaluate the robustness of study findings without multiple imputation vs. those with imputation or from pattern-mixture modeling.

Zoom IRB Boilerplate:

Zoom is a secure, user-friendly, cloud-based enterprise videoconferencing service that Ohio State University implemented in 2018. Zoom is accessible to faculty and staff at all Ohio State campuses via <https://carmenzoom.osu.edu> .

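### Total gain stops at 35-37 weeks but is judged against whole-pregnancy IOM limits, so excessive gain is under-counted if women gain after T3; healthy gain is left undefined

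*Combined protocol and SAP*

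**What the plan says.** All references are to the combined protocol and SAP.

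- **Limits.** Section C, Primary outcome, presents the IOM ranges as limits on total gain: "The IOM recommends that overweight women (BMI 25.0-29.9) be limited to total GWG of 15-25 lbs", and 11-20 lb for obese women. A woman whose total gain is above her limit is classed as excessive.
- **Measurement.** The same paragraph says: "To compute the total GWG, we will subtract the self-reported pre-pregnancy weight from weight measured at T3". Section A, Research Design, places that visit "at 35-37 week-gestation (T3").
- **Use.** The primary hypothesis in section I is: "A higher proportion of intervention participants will have healthy gestational weight gain than the usual prenatal care participants". Section F, Aim 2, uses logistic regression for the "probability of having a binary outcome (for example, excessive gestational weight gain" being the first example given).
- **Background rate.** Section II, A.1, gives the frequency of excessive gain as "65-85% for overweight or obese vs. 34% for normal weight".
- **Later weights.** Section C says: "Primary and secondary outcomes will be extracted from electronic health record". Under Usual care, section D says that "pregnant women are weighed at each prenatal visit", and visits are weekly from 36 weeks to delivery.

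No section scales the limits to gestational age, extrapolates to delivery or uses a weight after T3. Only excessive gain is defined; healthy gain is not.

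**The concern.** A gain that leaves out the last weeks of pregnancy is set against a limit for all of it. A woman under her upper limit at T3 who crosses it before delivery is recorded as not excessive. If no woman lost weight after T3, the T3 count could only be equal to or below the count at delivery. The recorded rate also depends on where in the two-week window she was weighed.

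The effect on healthy gain depends on a definition that the plan does not give. If healthy means not excessive, every woman missed as excessive is counted as healthy. If it means within the IOM range, the cut-off brings some women down into the range and drops others below it.

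At stake are the absolute excessive-gain rate, the healthy-gain comparison in the primary hypothesis, and the planning of the later trial, since section B says this pilot's estimates will guide its sample size.

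**Working it through.** **The plan's own power figure.** Inputs from section B: 36 per group, difference 0.33 lb/week, SD 0.55 lb, correlation 0.7 between two measures, two-sided 0.05.

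- SD of the average of two measures = 0.55 × √((1 + 0.7)/2) = 0.507 lb.
- Power = Φ(0.33/(0.507 × √(2/36)) − 1.96) = Φ(0.80) = 0.79, close to the stated 80%.
- No IOM limit enters this calculation, so the point does not touch weekly GWG or its power.

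**Inputs for the classification.** From the documents: excessive rates of 65-85%, and range widths w of 25 − 15 = 10 lb (overweight) and 20 − 11 = 9 lb (obese). Assumed, because the documents do not give them: total gain is normal with SD 10-15 lb, and m lb is gained after T3. With T3 at 36 weeks, delivery at 39 and 0.5-1.0 lb/week, m = 3 × 0.5 to 3 × 1.0 = 1.5-3 lb. A wider range is 0-5 lb.

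**Formulas.** For a true excessive rate p, let z = Φ⁻¹(p) − m/SD.

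- Recorded excessive rate = Φ(z).
- Recorded proportion within range = Φ(z + w/SD) − Φ(z).

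**Excessive gain within an arm.**

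- p = 75%, SD 12: Φ(0.674 − m/12) gives 70.9% (1.5 lb), 69.4% (2 lb) and 66.4% (3 lb).
- p = 65-85%, SD 10-15, m = 1.5-3 lb: the under-count runs from about 2.5 points (85%, SD 15, 1.5 lb) to 11.6 points (65%, SD 10, 3 lb).
- m = 0 gives 0; m = 5 lb gives at most 19.6 points.
- Timing (75%, SD 12, delivery at 39 weeks): a weight at 35 weeks misses 4 weeks of gain and one at 37 weeks misses 2. The recorded rates are 69.4% and 72.3% at 0.5 lb/week (2.9 points apart), and 63.3% and 69.4% at 1.0 lb/week (6.1 points apart).

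**Healthy gain within an arm, read as within range.** SD 12, m = 2 lb:

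| True excessive rate | Shift, w = 9 | Shift, w = 10 |
|---|---|---|
| 75% | +2.9 | +3.2 |
| 45% | +0.8 | +1.0 |
| 35% | −0.4 | −0.3 |

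At 65-85% excessive gain and 1.5-5 lb missed, the shift was upward in every case run (smallest +1.2 points). The sign changes at p = Φ((m − w)/(2·SD)). Here that is Φ(−7/24) = 38.5% for w = 9 and Φ(−8/24) = 36.9% for w = 10.

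**Between-arm differences, equal missed gain.** Assumed pairs of true excessive rates (usual care/intervention) are 85/65, 75/55, 75/45 and 65/45, with SD 10, 12 or 15.

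- Example, 75/55, SD 12, w = 10, m = 3 lb. Healthy: 28.12 − 18.42 = 9.7 points becomes 31.03 − 23.14 = 7.9. Excessive: 20.0 becomes 66.44 − 45.05 = 21.4.
- m = 1.5-3 lb: the healthy difference changes by +0.3 to −4.4 points.
- m = 0-5 lb: the healthy difference changes by +0.3 to −8.7 points (the extreme is at 5 lb and SD 10), and the excessive difference by −1.1 to +5.0.
- With m = 1.5, 2, 3, 4 and 5 lb there are 4 × 3 × 5 × 2 = 120 combinations. The healthy difference moved more than the excessive difference in 81 of them.

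**Between-arm differences, unequal missed gain.** If the planned 0.33 lb/week difference lasted three weeks beyond T3 (an assumption), the intervention arm would miss 3 × 0.33 ≈ 1 lb less. With 3 lb missed in usual care and 2 lb in the intervention arm (75/55, SD 12), the excessive difference goes from 20.0 to 66.44 − 48.36 = 18.1 points. Over the four pairs at SD 12 it shrinks by 0.2-3.1 points.

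**The case against.** **T3 is a defensible end point.** It lies near the end of a 20-week intervention that starts by 17 weeks, it is nearly common to all women, and it does not depend on delivery timing, which is tied to the premature-birth outcome. This stands as a reason to keep a T3 analysis. It does not justify calling that gain total, or setting it against limits for the whole pregnancy.

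**The size is assumed throughout.** Late gain, delivery week and SD all come from outside the documents, and the range includes no effect. This stands: the mismatch is certain, its size is not.

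**The consequence is small for a pilot.** In the 75/55 example the healthy difference moves by 1.8 points. With 36 per arm its standard error is √(0.184 × 0.816/36 + 0.281 × 0.719/36) = 9.9 points. This stands for any single test. A definitional shift does not shrink with sample size, however, and would carry into planning for the larger trial.

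**Stronger readings that a reader might infer.**

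- That the powered outcome or its 80% power is compromised. It is not; weekly GWG uses no IOM limit.
- That the rule favours the intervention. The documents do not support this. Under equal missed gain the healthy difference mostly shrinks and the excessive difference may move slightly either way. If the intervention arm gains less after T3, the excessive difference shrinks as well.
- That healthy gain is as likely to shift down as up. At the cited 65-85% it shifts up; a downward shift needs a rate of about 35%, and is then small.
- That healthy gain is hardly affected because it shifts less. That holds only for the proportion within an arm and only under the within-range reading. The primary hypothesis compares arms, and that difference often moves more than the one for excessive gain.

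**Conclusion.** The point holds. Gain to 35-37 weeks is compared with unscaled limits for total pregnancy gain, and nothing in the plan corrects it. If women gain on average after T3, the excessive-gain rate is under-counted, by about 2.5-12 points under the assumptions shown (normal total gain, SD 10-15 lb, 1.5-3 lb missed, true rates of 65-85%). With no late gain there is no average under-count.

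Healthy gain must be defined before its error can be stated. Read as not excessive, it is over-counted by the full amount. Read as within range, the arm proportions rise by less, and the between-arm difference is about unchanged or falls by up to about 4 points (about 9 at 5 lb and SD 10), provided that missed gain is equal in the two arms.

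This should be fixed, but it does not threaten the powered analysis. Error in self-reported pre-pregnancy weight is a separate problem that may add to or offset this one.

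**What to change.** 1. Define healthy gain as gain within the IOM range for the woman's BMI class.
2. For the IOM classification, use the last health-record weight before delivery minus pre-pregnancy weight, and record the date and gestational age of that weight. Keep the T3 weight for weekly GWG.
3. Report the T3-based classification as a sensitivity analysis labelled as gain to 35-37 weeks.
4. As a minimum, if T3 stays the main end point, use that label and do not report the result as total pregnancy gain.

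Do not adjust the main arm comparison for gestational age at the last weight, because it arises after randomisation and is tied to premature birth.

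**Cost.** One dated health-record field, a wording change and one sensitivity analysis; near-term weights should already exist from the routine visits.

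**Downsides.**

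- The outcome then depends partly on when a woman delivers.
- A few women who deliver elsewhere may lack a late weight, since section B requires only a plan to deliver at the study's medical center.
- Sections C (Lifestyle behaviors) and E suggest that study staff measure the T3 weight, while section C (Primary outcome) takes weights from the record. If T3 weights are study-measured, the last clinic weight is less standardised; if they come from the record, this drawback does not arise.

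The change does not remove error in the self-reported starting weight.

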Inclusion criteria. Participants must be pregnant women ≤ 13 week-gestation with a single fetus as assessed by ultrasound (Research staff or [name], Co-I, a board-certified Ob/Gyn at a collaborating clinic will verify eligibility from the patient's Electronic Health Record, EHR). Participants must also have self-reported (1) pre-pregnancy body mass index (BMI) of 25.0-45.0 kg/m² and height (we will use height and weight to compute body mass index). (2) ability to read and speak English, (3) age of 18-45 years, (4) access to a working smart phone with unlimited text messaging (89 to 94% of American adults aged 18 to 49 years own a smart phone)⁹⁷ and access to internet and (5) receipt of prenatal care and from our collaborating clinics and plan to deliver the baby at The Ohio State University (OSU) Wexner Medical Center, 6) a resident of Franklin Count, and (7) committed to the 20-week intervention.

Exclusion criteria. Self-reported (1) history of ≥ 3 miscarriages, (2) planned termination of the pregnancy, (3) diagnosed hypertension and type 1 or 2 diabetes, (4) history of or current diagnosis of an eating disorder, (5) serious current physical disease (e.g., renal disease or cancer), (6) past bariatric surgery, (7) current or history of substance abuse in the past 6 months, (8) current treatment for a serious psychological disorder (e.g., schizophrenia and bipolar disorder) or (9) contraindications to walking. Consented women will become not eligible to participate in the study if they are not randomized by 16-week 6 days gestation (see D. Detailed Study Procedure: Recruitment and enrollment)—this is because the study intervention starts ≤ 17 weeks gestation. Also, women will become not ineligible for participation if they did not complete the baseline data (T1): online survey via REDCap, two 24-hour dietary recall and wear the Actigraph monitor for at least 4 consecutive days with 6 hours per day.

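### Excessive-gain analysis: prespecify weight gain up to T1 as a covariate, because it precedes randomisation yet counts in the outcome

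*Combined protocol and SAP*

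**What the plan says.** Section C (Primary outcome) defines two quantities. Weekly GWG is the change in measured weight between adjacent visits, T1 to T2 and T2 to T3, per week. Total GWG is different: "we will subtract the self-reported pre-pregnancy weight from weight measured at T3". Gain is excessive when this total passes the upper limit for the woman's class: "overweight women (BMI 25.0-29.9) be limited to total GWG of 15-25 lbs and obese women (BMI ≥ 30.0) to 11-20 lbs".

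On timing, section B makes consented women ineligible "if they are not randomized by 16-week 6 days gestation", and they must complete the baseline data first. T1 is the baseline assessment (up to 15 weeks in the Research Design, up to 16 weeks in section C). T3 is at 35 to 37 weeks.

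Section F, Aim 2, uses logistic regression for binary outcomes ("for example, excessive gestational weight gain, gestational hypertension, new born body weight), adjusting for covariates (e.g., race"). Race is the only covariate named, and the list is open. Section D stratifies randomisation by race alone.

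The sample-size paragraph concerns weekly GWG only: 72 women "will have 80% power to detect a time-averaged between-group difference in weekly GWG".

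**The concern.** Total GWG splits exactly into two parts:

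total GWG = (T1 weight − self-reported pre-pregnancy weight) + (T3 weight − T1 weight).

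The first part is settled before allocation. It also carries the error in the self-reported weight. In the excessive-gain comparison it adds variation that treatment cannot influence, and a model with race alone leaves that variation in the error. A baseline quantity that forms part of the outcome by arithmetic is an obvious covariate, and naming it beforehand avoids choosing covariates after the data are seen.

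This matters because the primary hypothesis in section I is worded as a proportion of women with healthy gain, and excessive gain is the first example given for the logistic model. The estimates are also meant to inform the sample size of a later full-scale trial.

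**Working it through.** **1. The plan's own figure.** Inputs from Sample size/power: SD 0.55 lb, correlation 0.7, "between-group difference of 0.33 lb in weekly GWG" ("standardized between-group difference of 0.6"), 36 per group, "two-sided significance level of 0.05".

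- SD of the mean of two measures: 0.55 × √((1 + 0.7)/2) = 0.507 lb.
- Standard error of the difference: 0.507 × √(2/36) = 0.1195, so z = 0.33/0.1195 = 2.76.
- Power = Φ(2.76 − 1.96) = 78.8%. Attrition: 72/(1 − 0.20) = 90.

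The stated 80% reproduces approximately. This calculation contains no weight gained before T1.

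**2. The same effect carried to total gain.** Assume 10 weeks from T1 to T2 and 10.5 from T2 to T3.

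- Treatment effect: 0.33 × 20.5 = 6.8 lb.
- SD of gain after T1: 0.55 × √(10² + 10.5² + 2 × 0.7 × 10 × 10.5) = 10.4 lb.

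**3. Size of the early component.** Its SD, including self-report error, is not in the documents; 3 to 10 lb is assumed. If early and later gain are uncorrelated, its share of the variance of total gain is SD²/(SD² + 10.4²):

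- 3 lb: 9/117 = 8%
- 8 lb: 64/172 = 37%
- 10 lb: 100/208 = 48%

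The 95% range for chance imbalance between arms is ±1.96 × SD × √(2/36): ±1.4 lb at 3 lb, ±3.7 lb at 8 lb and ±4.6 lb at 10 lb.

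**4. Power for excessive gain.** Simulation: 3,000 trials per row, 36 per arm, 0.33 lb/week, likelihood-ratio test of treatment. Control rates span the 65 to 85% that section II (A.1) gives for overweight or obese women. Further assumptions: half the women obese, equal gain in both BMI classes, normal distributions, race not prognostic.

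| Early-gain SD (lb) | Control rate | Correlation early/later | Race only | + gain to T1 | + gain to T1 and BMI class |
|---|---|---|---|---|---|
| 4 | 65% | 0 | 51% | 56% | 57% |
| 4 | 75% | 0 | 51% | 55% | 56% |
| 4 | 85% | 0 | 46% | 48% | 50% |
| 8 | 65% | 0 | 39% | 49% | 51% |
| 8 | 75% | 0 | 40% | 48% | 50% |
| 8 | 85% | 0 | 34% | 42% | 42% |
| 10 | 65% | 0 | 34% | 49% | 50% |
| 8 | 75% | 0.3 | 33% | 46% | 47% |

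As a check on the 8 lb, 75%, uncorrelated row, the implied rates are 75.1% and 56.8%. The two-proportion formula gives Φ((0.183 − 1.96 × 0.1117)/0.1096) = 37%, close to the simulated 40%.

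The ends of the range come from further runs. At 3 lb, power went from 52% to 55% (control rate 75%) and from 46% to 48% (85%). At 10 lb with correlation 0.3, control rate 75%, two 10-week intervals and race left out of both models, it went from 24% to 43%.

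**5. Contribution of BMI class.** Added to race alone, it gives 0 to about 3.5 points. If obese women gain 5 lb less after T1, it adds almost nothing, because the lower limit offsets the lower gain.

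**6. Cost in type I error.** With both covariates the likelihood-ratio test rejected a true null in about 5 to 8.6% of trials, against at most about 6.5% with race only. The excess appears when few women avoid excessive gain: at 85% in both arms, 72 × 0.15 ≈ 11 women support four terms (treatment, race, gain, class). Holding size at 5%, the 8 lb, 75%, uncorrelated row goes from 37% to 46%. Across the scenarios in which size was adjusted, the rise was about 2.5 to 17 points.

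**The case against.** The strongest reply is that the primary analysis already avoids the problem. The powered outcome is weekly GWG, which uses measured weights from T1 onward. That stands: a reader might infer that the main analysis is diluted by gain before randomisation, and the documents do not support that.

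A reader might also infer that the model excludes these covariates or gives a biased comparison. Neither follows. The covariate list is open, so the gap is only that gain to T1 is not named in advance. Randomisation protects the unadjusted comparison, and chance imbalance is already reflected in its confidence interval. What is lost is precision.

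The size is fairly challenged too. An SD of 10 lb implies a 95% span of about 39 lb (2 × 1.96 × 10) in apparent gain by T1, against whole-pregnancy limits of 20 to 25 lb, so the upper end is doubtful. The calendar share before randomisation, up to 16.9/37 to 16.9/35 or about 46 to 48%, is a latest-case share of time, not of weight.

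Nor can it be said that the covariate is known at baseline for every woman. Section B's list of baseline data required for participation covers the survey, dietary recalls and Actigraph wear, but not weight. Weight comes from the health record.

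Finally, this is a pilot that disclaims power for smaller effects, and its hypothesis concerns healthy gain, which is not simply the complement of excessive gain. That limits the weight of the point, but estimates intended to inform a later trial still benefit from precision.

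**Conclusion.** The point holds as a cheap improvement to one comparison. Total GWG contains a component fixed before randomisation, and section F should name it as a covariate for excessive gain.

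For an assumed early-gain SD of 3 to 10 lb, power rises by roughly 2 to 19 points. The top of that range needs both the largest SD and a correlation of 0.3 with later gain. At 8 lb and a 75% control rate without correlation, the rise is about 10 points. Gain to T1 supplies nearly all of it.

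A reader might infer that adjustment makes the comparison adequately powered or comes at no cost. Adjusted power stayed below 60% in every scenario, and the likelihood-ratio test was somewhat liberal in sparse settings. Nor does adjustment repair misclassification: the covariate and the outcome use the same self-reported weight, so the model absorbs its noise but leaves some women on the wrong side of the limit.

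**What to change.** In section F, Aim 2, for the excessive-gain model:

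- Prespecify gain to T1 as a continuous covariate alongside race: the last clinic weight in the electronic health record on or before the day of randomisation, minus self-reported pre-pregnancy weight.
- Treat pre-pregnancy BMI class (25.0–29.9 versus 30.0 or more) as an optional second term.
- State that this weight predates randomisation, and how a missing one is handled.
- Test treatment with a small-sample method, such as Firth-penalised likelihood or a permutation test respecting the race strata.
- Report the standardised (marginal) risk difference with its 95% CI, so that the estimate keeps its population meaning after adjustment.

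The outcome definition and the weekly-GWG analysis stay as they are. The cost is a few sentences, one or two model terms and a dated weight from the health record, which the plan already uses as its source of body weight.
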